9.2.1 Suspected unexpected serious adverse reactions (SUSAR)

Chapter-9.2.2 is not applicable for this study.

Adverse reactions are all untoward and unintended responses to an investigational product related to any dose administered.

Unexpected adverse reactions are adverse reactions, of which the nature, or severity, is not consistent with the applicable product information (e.g. Investigator's Brochure for an unapproved IMP or Summary of Product Characteristics (SPC) for an authorised medicinal product).

The sponsor will report expedited the following SUSARs through the web portal *ToetsingOnline* to the METC:

- SUSARs that have arisen in the clinical trial that was assessed by the METC;
- SUSARs that have arisen in other clinical trials of the same sponsor and with the same medicinal product, and that could have consequences for the safety of the subjects involved in the clinical trial that was assessed by the METC.

The remaining SUSARs are recorded in an overview list (line-listing) that will be submitted once every half year to the METC. This line-listing provides an overview of all SUSARs from the study medicine, accompanied by a brief report highlighting the main points of concern.

The expedited reporting of SUSARs through the web portal *ToetsingOnline* is sufficient as notification to the competent authority.

The sponsor will report expedited all SUSARs to the competent authorities in other Member States, according to the requirements of the Member States.

The expedited reporting will occur not later than 15 days after the sponsor has first knowledge of the adverse reactions. For fatal or life threatening cases the term will be maximal 7 days for a preliminary report with another 8 days for completion of the report.

9.3 Annual safety report

In addition to the expedited reporting of SUSARs, the sponsor will submit, once a year throughout the clinical trial, a safety report to the accredited METC, competent authority, Medicine Evaluation Board and competent authorities of the concerned Member States.

This safety report consists of:

- a list of all suspected (unexpected or expected) serious adverse reactions, along with an aggregated summary table of all reported serious adverse reactions, ordered by organ system, per study;
- a report concerning the safety of the subjects, consisting of a complete safety analysis and an evaluation of the balance between the efficacy and the harmfulness of the medicine under investigation.

9.4 Follow-up of adverse events

All adverse events will be followed until they have abated, or until a stable situation has been reached. Depending on the event, follow up may require additional tests or medical procedures as indicated, and/or referral to the general physician or a medical specialist.

9.5 Data Safety Monitoring Board (DSMB)

Due to the short duration of the study, no Data Safety Monitoring Board will be appointed.

10 STATISTICAL ANALYSIS

10.1. Descriptive statistics

Data will be expressed both quantitatively (values of PCr, ATP, Pi, pH, rate constants tau_PC_r and tau_Pi, expressed as median and range), and qualitatively (MRS-spectra).

10.2 Univariate analysis

Results will be presented by means of confidence intervals. The significance level will be set at $p < 0.05$. Statistical analysis of the results will be performed using standard two-sided Mann-Whitney testing and will be conducted using Origin software (Caltech, USA, version 6.1).

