Collaboration with the Dutch VLCADD expertise centre

Since 2007 Very Long Chain Acyl-CoA Dehydrogenase Deficiency (VLCADD) is included in the Dutch neonatal screening program (NSP). VLCADD is a rare disease (1:80000) and has only been discovered recently in 1992. Knowledge about disease course and long term effect of therapy is scarce. Therefore, the UMC Utrecht in collaboration with the Laboratory Genetic Metabolic Diseases (Academic Medical Center Amsterdam) and RIVM started an expertise centre in which all patients with VLCADD in the Netherlands can be seen. The primary goal of this expertise center is to document the clinical and biochemical phenotype and disease course of all diagnosed VLCADD patients in the Netherlands (METC nr 10-430/C). The Center partakes in the present investigative team to investigate the clinical benefits of acute NK in human VLCADD ([name]). The PI of the present application ([name]) has

previously collaborated with the center in a clinical investigation into muscle ATP metabolism in VLCADD patients (protocol **12-211/K** (UMC Utrecht)).

Inclusion of adolescent patients

Due to the rarity of the disease this study will include patients from the age of 16 years that could benefit from NK as well. Since rhabdomyolysis often has an onset in adolescence, confirmation of our hypothesis would lead to therapeutic use in that age group as well. Moreover, older patients often suffer from severe exercise intolerance and loss of muscle function due to earlier episodes of rhabdomyolysis, leaving most of them unable to complete our study protocol. Originally, all adult VLCADD patients known by the Dutch expertise center were provided with information on the study. Unfortunately, 1.5 years after the first inclusion only four patients participated. The main reason the other patients did not want to participate was the intensity of the protocol. Although the exercise test is at moderate intensity, the physical condition of these patients withholds them from riding a bike. Therefore an amendment was made to the original protocol to lower the minimum age to 16 years to reach sufficient power for this study. Unfortunately not many adolescent patients are known in The Netherlands, lowering the minimum age to 16 years will make participation possible for one patient. Lowering the minimum age even further won't make a difference, since the patients between 10-16 years are both rare and severely affected.

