3. STUDY DESIGN

This is a randomised, blinded, placebo controlled, two-way cross over trial. Patients with VLCADD will be recruited by the VLCADD Expertise Center at UMC Utrecht. Nutritional ketosis will be compared to a placebo, delivered as an isocaloric drink before exercise. An individualised, standardised bicycle exercise protocol will be completed by each participant with collection of blood metabolites, respired gases, and subjective ratings of fatigue and muscle complaints. In addition in vivo ³¹P MR Spectroscopic recordings will be made from the quadriceps muscle before (resting), during and post-exercise. An optional muscle biopsy will be obtained from the quadriceps before and after exercise.

Patients will be asked to participate in three study sessions:

session I (site: nearest Academic Medical Center, Pediatric test ward).

- standard maximal cardiopulmonary exercise test (CPET; bicycle ergometry with indirect calorimetry)
objective: determination of VO_{2max} in order to set the desired exercise workload of maximal individual rate of fat oxidation (FATMAX; typically ~40% MVO_2) in sessions II and III below.
- venipuncture
objective: measure rise in blood lactate and creatine kinase (CK) levels in response to CPET

sessions II and III (site: Neuroimaging Magnetic Resonance Center UMC Groningen).

- venipuncture + canulation
objective: prepare subject for serial (every 10 min) blood sampling for off-site metabolic profiling
- oral intake of nutritional drink A or B (ketone and placebo drinks, respectively)
Each subject will receive both drinks over the course of the trial in a blinded fashion – i.e., if drink A in session II, then drink B in session III, and vice versa.
- microbiopsy from the quadriceps muscle (optional)
*1st biopsy: 20 min after oral drink; 2nd biopsy: immediately following end of exercise bout.
objective: metabolomic profiling of the state of the energy metabolic network in muscle and mapping of individual phenotypic muscle properties (fiber type, mitochondrial density, capillary density). Biopsies will be obtained from the m. vastus lateralis of the left leg. Hereto, a preparatory superficial incision of the skin and fascii will be made under local sedation and bandaged, allowing fast and reproducible biopsy sampling prior to and immediately following exercise bout 1 below.*

- 40 min upright bicycling exercise at FATMAX outside MR scanner (exercise bout 1)

Blood samples are collected every 10 minutes.

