4.4 Sample size calculation

Exact sample size calculation for this study is difficult for several reasons:

1. VLCADD is a rare metabolic disorder. The UMCU Center currently has 6 patients that may qualify for this particular study.
2. The proposed study is the very first of its kind. No equivalent means of imposing acute NK has previously been available. As such, there are no data available on the magnitude of any enhancement effect of the nutritional intervention on metabolic performance in this particular group of patients.

As mentioned in Section 3, this study is a randomised, blinded, placebo controlled, two-way cross over trial. In previous case-control design studies, it has been well established that $\geq 30\%$ differences in the two categories of MRS-derived metabolic parameters – i.e., steady-state muscle pH, Pi and PCr levels, and kinetic rate constants of metabolic recovery post-exercise - can be reliably and reproducibly identified by the proposed investigational methods (e.g. [18]). We previously successfully detected statistically significant abnormalities in muscle MRS parameters ($P < 0.05$; two-sided) in a case-control study of VLCADD featuring 5 patients (Diekman et al, PloS One 2016).

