8.2 Randomisation, blinding and treatment allocation

Patients will be handed an unlabeled caloric drink (placebo and ketone ester drink) prior to the endurance exercise bout in each of the two study sessions at UMCG. All patients will receive both drinks over the course of the study. [name], who will

conduct the studies at UMCG together with PI [name], will plan, randomize and record the order of placebo and ketone ester administration to the patients. [name], who will analyze all MRS data, will not have, nor seek access to, these records thus ensuring blinded MRS data analysis.

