10.3 Multivariate analysis

not applicable

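### The only test named, the unpaired Mann-Whitney test, does not fit a cross-over in which every patient receives both drinks, and it is too strict if a patient's two sessions are positively correlated

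*Protocol*

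**What the plan says.** Section 3 of the protocol sets the design: "This is a randomised, blinded, placebo controlled, two-way cross over trial". Section 8.2 confirms the pairing: "All patients will receive both drinks over the course of the study". The main endpoints in section 8.1.1 (muscle Pi, PCr and pH during exercise versus rest, and post-exercise recovery rate constants) are continuous and measured in both treatment sessions.

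For the analysis, section 10.2 states: "Statistical analysis of the results will be performed using standard two-sided Mann-Whitney testing". The significance level there is 0.05, and confidence intervals are promised without saying for which quantity. Section 10.3 (Multivariate analysis) is "not applicable". Section 10 contains no paired test, within-patient difference or period term.

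The precedent in section 4.4 is a significant result "in a case-control study of VLCADD featuring 5 patients", which compares independent groups.

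On numbers, section 4.1 plans six patients. Section 1 reports: "Unfortunately, 1.5 years after the first inclusion only four patients participated", and adds that "lowering the minimum age to 16 years will make participation possible for one patient".

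**The concern.** Mann-Whitney takes its null distribution from two independent samples. Here both sets of values come from the same people. When a patient's two sessions are positively correlated, stable differences between patients cancel out of the treatment comparison, but Mann-Whitney still counts them as noise. The test then rejects too rarely under the null and misses real effects.

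This is not a detail left to a SAP. The protocol itself fixes a test that contradicts its own design. The test would suit the earlier patient-versus-control study, but not this trial.

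At stake is the power of the main comparison in six patients, perhaps five. Section 1 justifies lowering the minimum age to 16 by the need for sufficient power, and shows that the pool of patients is nearly exhausted. Power lost in the analysis cannot be recovered by recruiting.

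**Working it through.** **Inputs from the protocol.** Two-way cross-over (section 3); both drinks in every patient (8.2); six patients (4.1); two-sided Mann-Whitney at 0.05 (10.2). Section 1 gives four participants plus one newly eligible, so n = 5 is also examined. There is no stated power or calculated sample size to reproduce; section 4.4 calls an exact calculation difficult.

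**Assumptions.** CV 15–30%, within-patient correlation ρ from 0 to 0.8, and a true difference of 30% of the placebo mean. Section 4.4 mentions 30% as a difference that the methods can detect in case-control studies, not as an expected effect, so it is illustrative here. Data are bivariate normal with equal variances, with 100,000 or more simulated trials per cell.

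**1. Exact Mann-Whitney size if the samples were independent.**
- 6 v 6: reject at U ≤ 5. The one-tail count is 1+1+2+3+5+7 = 19 of 924, so the size is 2×19/924 = 0.041.
- 5 v 5: reject at U ≤ 2. The count is 1+1+2 = 4 of 252, so the size is 2×4/252 = 0.032.

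**2. What correlation changes.** The SE of the mean difference is σ√(2(1−ρ)/n); treating the samples as independent implies σ√(2/n). With σ = 25%, ρ = 0.7 and n = 6, the true SE is 25×√(0.6/6) = 7.9%, and the independent-samples value is 25×√(2/6) = 14.4%.

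**3. True type I error of Mann-Whitney at nominal 5%.**

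| ρ | 0 | 0.3 | 0.5 | 0.7 | 0.8 |
|---|---|---|---|---|---|
| n = 6 | 4.1% | 2.1% | 1.1% | 0.4% | 0.2% |
| n = 5 | 3.2% | 1.6% | 0.8% | 0.3% | 0.1% |

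The paired t-test held about 5% throughout.

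**4. Power for a 30% difference, Mann-Whitney v paired t.**

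| CV, ρ | n = 6 | n = 5 |
|---|---|---|
| 15%, 0.5 | 88% v 97% | 71% v 91% |
| 25%, 0.7 | 41% v 85% | 26% v 74% |
| 30%, 0.8 | 26% v 87% | 15% v 75% |

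Further cells at n = 6: 62% v 83% (CV 20%, ρ 0.5) and 40% v 52% (CV 25%, ρ 0.3). At ρ = 0 pairing gains nothing: 83% v 79% (CV 15%) and 41% v 39% (CV 25%). Over CV 15–30% and ρ 0.5–0.8, Mann-Whitney spans 26–91% and paired t 51–100% at n = 6; at n = 5 the spans are 15–72% and 40–100%.

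Analytic check of one cell (CV 25%, ρ 0.7, n = 6): the noncentrality is 30/7.9 = 3.8 on 5 df, which gives 85%, as simulated.

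**5. Could the text mean a valid cross-over use of Mann-Whitney?** One can compare within-patient period differences between the two drink orders. The protocol does not say so. With three patients per order the smallest two-sided p is 2/20 = 0.10, so 0.05 could not be reached.

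**6. Limits of the obvious rank alternative.** The smallest two-sided p of the Wilcoxon signed-rank test is 2/2ⁿ: 0.031 at n = 6, 0.0625 at n = 5 and 0.125 at n = 4.

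**The case against.** - **Direction.** The test is too strict only under positive correlation. At ρ = −0.3 its type I error is 6.8% with six patients. This stands as a condition. Positive correlation is the expected case for repeat muscle measurements in one person, but the protocol gives no value.
- **Illustrative effect.** The protocol assumes no treatment effect, and a 30% change is not a sensible scenario for pH. This also stands: the power figures show scale and are not a forecast.
- **Normality favours the t-test.** With log-normal data and a multiplicative 30% effect (CV 25%, ρ 0.7), paired t falls to 74% at n = 6 and 60% at n = 5. Mann-Whitney falls too, to 31% and 19%, so the gap remains. Normality cannot be checked with five or six differences, and moving from ranks to a t-test is a choice beyond pairing.
- **Severity.** The study is a small mechanistic first test, confidence intervals are promised, and nothing is lost at zero correlation. But the named test governs the main endpoints, the mismatch with the design does not depend on ρ, and correction is cheap.

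**Conclusion.** The point holds and must be fixed. The protocol's only named test is for independent groups, and the data are paired by design. That conclusion needs no assumption.

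The size of the harm does. Under positive correlation the error is towards missing an effect; no excess of false positives is claimed for that case. The loss of power runs from none at ρ = 0 to about 60 percentage points at CV 30% and ρ 0.8 (87 − 26 = 61 at n = 6; 75 − 15 = 60 at n = 5). Six patients is the planned number; five is an inference from section 1.

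**What to change.** In section 10.2, replace Mann-Whitney with a within-patient analysis of the ketone-minus-placebo difference for each main endpoint: a paired t-test, reported with the mean difference and its 95% CI. Name this as the single main analysis. A linear model with patient, drink and period can be added as a sensitivity analysis if both drink orders are represented. Do not make the signed-rank test or a sign-flip permutation test the sole test, because neither can reach p<0.05 with five or fewer patients. Median and range can stay as descriptive summaries.

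**Cost.** One paragraph of wording, with no change to patients, allocation or measurements. The paired t-test relies on approximately normal differences in a very small sample. Period adjustment costs some power: at CV 25% and ρ 0.7, from 85% to 81% with six patients and from 74% to 63% with five. Because patients had already taken part, and section 12.2 refers to analysis of the first three, the change should be recorded as made without knowledge of results by drink and notified to the METC as an amendment under section 12.3.

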10.3 Multivariate analysis

not applicable

10.4 Interim analysis

Not applicable.

11. ETHICAL CONSIDERATIONS

11.1 Regulation statement

The study will be conducted according to the principles of the Declaration of Helsinki Brazil, October 2013, and in accordance with the Medical Research Involving Human Subjects Act (WMO).

11.2 Recruitment and consent

Patients will be informed about the study during follow-up visits to the outpatient clinic, or during the patient information day that is organized every year in the UMC Groningen. They will be recruited by means of information that is administered both orally, and written in a patient information letter. After information has been administered orally, potential participants will receive written patient information. The physician will inform the patients and supply the written patient information. Patients will be asked to reply to the request within 14 days after oral and written information has been provided. This period can be extended 14 days extra. If after 14 days patients didn't reply after the provided written information, they will receive a recall letter. If subjects don't respond after 14 days they will not be contacted any further. In order to approve of participation in the study, participants have to return the signed informed consent form by mail to the coordinating investigator. After the informed consent form has been received, the coordinating investigator will contact the participant by phone to provide further details if needed. All participants will be asked to sign a written consent form.

11.4 Benefits and risks assessment, group relatedness

In clinical practice, many patients with VLCADD wonder to which extent they are able to exercise safely. Any means of boosting this capacity will greatly improve the quality of life and long-term health in this patient population. Acute nutritional ketosis after ingestion of a novel edible ketone ester is a very promising novel therapy towards this aim and has already been tested with positive effects in human athletes. This study will gain insight whether a sound metabolic basis exists for its therapeutic use in this patient population.

No adverse effects of this study are expected. Of the listed interventions that are proposed here, all but one – i.e., ingestion of the ketone caloric drink - have previously been included and approved in clinical investigations of metabolic myopathy patients by members of the investigativce team in Amsterdam, Utrecht and/or Groningen: venipuncture and microbiopsy of the quadriceps muscle prior to and after exercise (protocol **04/1984 (MCADD; AMC Amsterdam)**); protocol **NL41313.042.12 (MCADD; UMCG)**); bouts of prolonged bicycle exercise outside and inside a MR scanner including in vivo MR spectroscopic data collection (protocol **12-211/K (VLCADD; UMC Utrecht; protocol NL41313.042.12 (MCADD; UMCG))**). Of the interventions, only the **burden** of collecting tissue samples from the quadriceps muscle by microbiopsy is rated as moderate (as opposed to ratings of nil to minor burden for

all other interventions²). As such, this intervention will only be performed on a voluntary basis; it will not affect enrollment in the study. Muscle tissue sampling is needed to test the secondary hypothesis that NK boosts muscular mitochondrial function specifically at the level of substrate supply to the TCA cycle; therefore, the burden of micro biopsy is considered justifiable.

The **safety** of the nutritional drinks that will be administered and the expected acute, transient mild ketosis (concentrations of ketone bodies < 3 mM) has been thoroughly tested and documented in healthy subjects (see references 9,10). The drink has been designated as 'GRAS' (= Generally Recognized as Safe) by the Federal Drug Administration of the United States allowing it to be used as a foodstuff in the USA. No particular risk for VLCADD patients is expected with respect to oral ingestion of the ketone ester since its metabolites are natural, organic compounds released without any cation or proton load that are readily oxidizable by cellular mitochondria irrespective of enzymatic defects in fatty acid oxidation.

The **benefit** to VLCADD patients of participation in the study is potentially enormous. In our previous applications for exercise and MRS testing in metabolic myopathy (protocols **12-211/K (VLCAD)**; UMC Utrecht) and **NL41313.042.12 (MCAD)**, respectively), we put forward that the benefit of those studies would be that it would help establish a platform to conduct studies on the effectiveness of medication. Here, we now exploit this validated platform to test the metabolic effects of a nutritional drink that may revolutionize therapy of human metabolic myopathies due to defects in carbohydrate or fat metabolism. Ultimately, an effective treatment for VLCADD may be available for the first time to improve the quality of life of patients, including the opportunity to engage in a more active lifestyle with generic (including cardiovascular and anti-diabetic) health benefits.

11.5 Compensation for injury

The sponsor/investigator has a liability insurance which is in accordance with article 7, subsection 6 of the WMO.

The sponsor (also) has an insurance which is in accordance with the legal requirements in the Netherlands (Article 7 WMO and the Measure regarding Compulsory Insurance for Clinical Research in Humans of 23th June 2003). This insurance provides cover for damage to research subjects through injury or death caused by the study.

² the short, maximum exercise test in session I will use anaerobic derived energy. As patients with VLCADD do not have a problem in glycolysis, the burden for this test will be nihil. The endurance test at submaximal level might induce muscle pain temporarily. the burden for patients is classified as minimal and patients will be monitored accordingly during the study period. Blood will be drawn intravenously from patients; this implies a minimal burden.

1. € 450.000,-- (i.e. four hundred and fifty thousand Euro) for death or injury for each subject who participates in the Research;
 2. € 3.500.000,-- (i.e. three million five hundred thousand Euro) for death or injury for all subjects who participate in the Research;
 3. € 5.000.000,-- (i.e. five million Euro) for the total damage incurred by the organisation for all damage disclosed by scientific research for the Sponsor as 'verrichter' in the meaning of said Act in each year of insurance coverage.
- The insurance applies to the damage that becomes apparent during the study or within 4 years after the end of the study.

